is caused by poor vasculated bone. Teeth with poor prognosis should be extracted before radiotherapy begins, leading to impaired occlusion including dysfunctional aesthetics and mastication. The Swedish National Board of Health and Welfare regulations compensate extracted teeth with removable dental prostheses/dentures (8). However, using removable dentures in patients with hyposalivation after radiotherapy is complicated. Removable dentures retain poorly, or chafe the oral mucosa leading to pain in function. Also, there may be problems maintaining good dental and denture hygiene leading to dental caries and periodontitis.

To date, the impact of dental occlusion on these patients' quality of life is sparsely investigated. In one study, implant-retained mandibular overdentures in patients treated for oral cancers were followed over five years (9). Overall, the survivors' oral function and patient satisfaction were high and did not change. Impaired global health and quality of life were associated with concurrent comorbidity. Malnutrition, associated with increased morbidity and mortality, in patients treated for oral/oropharyngeal cancers was shown to impair physical functioning and hence quality of life (10). In this study dental status was poorly described, although dry mouth, pain in the mouth, and problems with social contact correlated well to malnutrition and fatigue. Speech after surgery was more impaired in patients with oral cancers than with oropharyngeal cancers because of loss of anatomically important articulatory structures leading to decreased quality of life. However, there are no prospective studies supporting better speech outcome after radiotherapy alone compared with surgery (11).

Therefore, the aim of this project was to evaluate the effect and cost effectiveness of prosthodontic rehabilitation on oral health related quality of life, general wellbeing, and nutrition in patients treated by radiotherapy, with or without combination of

chemotherapy or surgery against head and neck cancer.

Methods

Design and setting

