The study will take place in four middle sized counties in the south of Sweden. The intervention will include 30 patients with head and neck cancer recruited from a Department of Maxillofacial and Oral Surgery (the City of Jönköping, Jönköping County Council), and from the Department of Orofacial Medicine (the City of Stockholm, Stockholm County Council). Another 30 patients with the same disease will be matched controls recruited from another Department of Maxillofacial and Oral Surgery (the City of Linköping, County Council of Östergötland) and from five Departments of Orofacial Medicine (the Cities of Kalmar, Oskarshamn, and Västervik, Kalmar County Council; the Cities of Ljungby, and Växjö, Kronoberg County Council). If possible but not necessary, those controls may be prosthodontically rehabilitated with temporary removable dentures. The retest described in data collection study one will include ten patients diagnosed with head and neck tumor. All patients in the retest will be residents in the County of Jönköping.

The inclusion criteria are patients with head and neck tumours considered to receive radiotherapy, with or without combination of chemotherapy or surgery, good oncological prognosis at baseline ($\leq T2$). After referral from an ENT-specialist, those patients being diagnosed with dental infections and therapy planned for dental extraction(s) will be included.

The following general exclusion criteria will be applied: any communication problems; any comorbidity with poor prognosis; poor oncological prognosis (TNM-classification $>T2$) at baseline; imminent risk of recurrence; any technical, biological, or any other reasonable obstacle of treating patients with fixed dentures; and finally patients in the matched control group financing fixed oral prosthesis themselves.

Background data like sex, age, diagnosis, TNM-classification, hyposalivation, vertical jaw mobility, dysphagia, number and sites of extracted teeth, and weight will be investigated.

Study one – quantitative approach

Instruments

SF-36v2

SF-36v2 is a well established psychometric instrument with 36 items measuring eight domains of health-related quality of life: Physical function, physical role function, bodily pain, general health, vitality, social function, emotional role function, mental health. The two comprehensive indices – physical health and mental health - can be estimated for. The instrument is translated and validated into Swedish (17-19).

EQ-5D

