EQ-5D is an instrument containing five items measuring mobility, self-care, pain, role function, and anxiety/depression. There is also one item considering change of health condition and a VAS scale for general health. This instrument is also translated and validated into Swedish (20-22).

Oral health impact profile (OHIP)

OHIP-14 is an instrument consisting of 14 items (23). It was designed to provide a comprehensive measure of the dysfunction, discomfort and disability attributed to oral conditions. Validated Swedish versions of the OHIP-14 are available (24, 25).

General oral health assessment index (GOHAI)

GOHAI is a 12-item instrument originally developed for use with older adult populations, although more recently it has been used with populations of younger adults. It measures oral functional problems and also assesses the psychosocial impacts associated with oral disease (26). A Swedish version has been validated (27).

The Jaw Functional Limitation Scale (JFLS-8)

The JFLS-8 was developed for assessing limitations in mastication, jaw mobility, and verbal and emotional expression. It is recommended for clinical and research use in patient groups with varying functional limitations of the jaw. The instrument has been tested for reliability and validity (28, 29).

The Orofacial Aesthetic Scale (OAS)

The OAS consists of seven separate aesthetic aspects of the face, teeth, lips, and mouth — devoid of psychosocial aspects. These seven items create the OAS summary score. There is also an eight item, global assessment of overall impact. A Swedish version has

been validated (28, 30, 31).

Data collection

The written consent among with the instruments will be distributed to the patients at the clinic at baseline (before any treatment), appendix 4. The completed documents will be returned to a research coordinator/dental assistant at the Department of

Maxillofacial and Oral Surgery (the City of Jönköping, Jönköping County Council).

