The first interview will take place approximately six months after completed radiotherapy, and the second one after approximately 12 months.

Data analysis

Qualitative content analysis described by Hsieh and Shannon (32) will be used in analysing the interviews. Each interview will be listened to in order to gain a general understanding of the content. Any content relevant to the aim will be analyzed. The text will be condensed and labelled using codes, being careful not to change the core of the meaning units based on the aims. The codes will be matched and grouped into

categories in accordance with similarities and dissimilarities. The categories will be scrutinised for underlying meanings, which will generate a number of sub-themes that reflect the content. The sub-themes will eventually be grouped under a few comprehensive themes.

Study three – validity and reliability test

Data collection

Eight patients with head and neck cancer from the Department of Maxillofacial and Oral Surgery (City of Jönköping), and eight healthy controls from the Public Dental Service Clinic (City of Jönköping) from study one will be recruited consecutively. The instruments described in study one will be completed at baseline. After 1-2 weeks, those patients (n=16) will complete the same instruments to evaluate test-retest reliability and validity.

Data analysis

Reliability

Homogeneity: Cronbach's alpha assesses internal consistency. According to Bland & Altman, Cronbach alphas of 0.70 to 0.80 are satisfactory for comparisons between groups, while an alpha of 0.90 is needed for clinical use.

Stability: Intraclass correlation coefficients (ICCs) with 95% confidence intervals are calculated per Shrout & Fleiss's ICC method based on a one-way analysis of variance (ANOVA). The concordance correlation coefficient (CCC) assesses reproducibility (temporal stability).

Validity

Content validity: Patients are asked, “Do you think the questions on aesthetics reflect the concerns you have with your mouth, your teeth and your tooth replacements (prostheses, crowns, bridges, and implants)?” They respond on a 0–10 VAS-scale with the anchors “very dissatisfied” and “very satisfied”.

Discriminative validity: Comparisons are made of OHIP-14 and GOHAI summary scores of each patient group with control groups and between patient groups. Relevant and statistically significant differences using t-tests and ANOVA are expected.

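### Study three does not ensure that the cancer patients are stable between test and retest, so the ICC and CCC may count real change as unreliability

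*Protocol*

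**What the plan says.** Four parts of the protocol bear on this.

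- **Study three, Data collection** names the sample: "Eight patients with head and neck cancer from the Department of Maxillofacial and Oral Surgery (City of Jönköping", together with "eight healthy controls from the Public Dental Service Clinic (City of Jönköping) from study one will be recruited consecutively". It sets the first form ("The instruments described in study one will be completed at baseline") and the second: "After 1-2 weeks, those patients (n=16) will complete the same instruments to evaluate test-retest reliability and validity".
- **Study one, Data collection** defines baseline for the patients. The instruments are "distributed to the patients at the clinic at baseline (before any treatment").
- **Participants** makes extraction part of eligibility: "those patients being diagnosed with dental infections and therapy planned for dental extraction(s) will be included".
- **Introduction** gives the order of care and its effect: "Teeth with poor prognosis should be extracted before radiotherapy begins, leading to impaired occlusion including dysfunctional aesthetics and mastication".

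Under Study three, Data analysis, stability is assessed with a one-way ANOVA ICC with 95% confidence interval and with the concordance correlation coefficient (CCC). The text does not say whether the 16 pairs are pooled or analysed by group, and it gives no acceptance limit for either coefficient. The limits quoted there belong to Cronbach's alpha.

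**The concern.** A test-retest coefficient estimates reliability only if the person's true state is unchanged between the two forms. Otherwise real change enters as disagreement. The one-way ICC has no term for occasion, so it charges both the average shift and the person-to-person variation in change to error. The CCC also penalises both.

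The protocol itself says that extraction impairs aesthetics and mastication. By its own descriptions of the instruments, the OAS covers aesthetics, the JFLS-8 covers mastication, and OHIP-14 and GOHAI cover oral dysfunction and functional problems. The questionnaires under test are thus the ones that should move if a patient has teeth removed between the forms.

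Two errors are possible. A sound instrument could look unstable in the patients. Or, if all 16 pairs are pooled, the difference between ill and healthy people could produce a reassuring coefficient that says little about stability in the patients. Design and setting forgoes a power calculation and relies on the supporting studies, this one included, to strengthen the main comparison.

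**Working it through.** **Timing, from the text**

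1. The first form is at baseline, before any treatment (Study three and Study one, Data collection).
2. The patients have planned extractions (Participants). Design and setting bases the methodological study on the case-control sample, so I take this condition to apply to the eight patients.
3. Poor-prognosis teeth should come out before radiotherapy (Introduction), that is, between baseline and radiotherapy.
4. The second form is 1-2 weeks after the first, counted from the same baseline.
5. The number of days from baseline to extraction or to radiotherapy is not stated.

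The retest is unaffected only if every patient's treatment comes after the second form. The text does not secure that.

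**Inputs for the illustration**

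The protocol gives no ICC, SD or expected change, so there is no figure of its own to reproduce beyond 8 + 8 = 16, which agrees with the stated n. (Participants gives ten retest patients; I use the eight of Study three.) All other values are assumptions, in units of the within-group SD of one score: true-score variance B = 0.85, error variance E = 0.15, and real change in patients with mean m and SD s, independent of the first score.

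**Patients only, two forms each**

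- MSW = (2E + s² + m²)/2
- MSB = 2(B + E/2 + s²/4)
- ICC = (MSB − MSW)/(MSB + MSW)
- CCC = 2B/(1 + 1 + s² + m²)

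| m, s | MSW | MSB | ICC | CCC |
|---|---|---|---|---|
| 0, 0 | 0.15 | 1.85 | 1.70/2.00 = 0.85 | 1.70/2.00 = 0.85 |
| 0.5, 0.5 | 0.40 | 1.975 | 1.575/2.375 = 0.66 | 1.70/2.50 = 0.68 |
| 0.8, 0.8 | 0.79 | 2.17 | 1.38/2.96 = 0.47 | 1.70/3.28 = 0.52 |

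With no change there is no bias.

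**Pooled, eight patients and eight unchanged controls**

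Let g be the patient-control gap at the first form, with patients worse and the change a worsening. The variances and covariance of the two forms over all 16 are:

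- v1 = 1 + (g/2)²
- v2 = 1 + s²/2 + ((g + m)/2)²
- c = B + (g/2)((g + m)/2)
- MSW = (v1 + v2 − 2c + (m/2)²)/2
- MSB = (v1 + v2 + 2c)/2

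For m = s = 0.5, MSW = 0.275 at every gap.

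| Gap g | MSB | Pooled ICC with change | Pooled ICC without change |
|---|---|---|---|
| 0 | 1.944 | 1.669/2.219 = 0.75 | 0.85 |
| 1 SD | 2.694 | 2.419/2.969 = 0.81 | 0.88 |
| 2 SD | 4.444 | 4.169/4.719 = 0.88 | 0.925 |

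Change always lowers the pooled value relative to no change at the same gap. But with a 2 SD gap the pooled ICC (0.88) exceeds the true within-group reliability (0.85), although the patients' own ICC is 0.66.

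**Precision**

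The Shrout-Fleiss 95% interval at an observed ICC of 0.80 uses F = 1.8/0.2 = 9, divided by the 97.5% point of F(n−1, n) for the lower limit and multiplied by that of F(n, n−1) for the upper; each result is converted by (F − 1)/(F + 1). It gives 0.53 to 0.92 for n = 16 and 0.33 to 0.96 for n = 8. If only four pairs remained, it would run from −0.05 to 0.99.

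**The case against.** The strongest objection is that the overlap is not written down. A reader might infer from the four passages that the retest definitely falls when extractions are done. The documents do not support that. The sentence on extraction before radiotherapy is background in the Introduction, not a schedule. No passage dates extraction from baseline, and the measurement schedule is referred to an appendix 13 that is not in the text at hand. If all extractions follow the second form, this bias does not arise. That stands, and it limits the point to a missing safeguard.

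A second tempting reading is that sound instruments will be judged unstable. Only the eight patients are exposed. A pooled coefficient may come out below or above the true reliability depending on the patient-control gap, and there is no ICC or CCC limit to fail. That stands too.

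Third, relevant data are partly planned: the number and sites of extracted teeth are background data, and the EQ-5D as described has an item on change in health. Neither is assigned to this use. The first carries no dates, and the second concerns general health rather than treatment between the forms.

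Fourth, the choice of pairs for an ICC could be left to an analysis plan. That is fair for the analysis rule. But the date of the second form and what is recorded with it are data collection, which the protocol fixes here. If treatment between the forms is not recorded, a later plan may be unable to separate the pairs.

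Last, this is a small supporting study of instruments described as largely validated already, and no rule makes the main comparison depend on its ICC. This limits the weight of the point but does not remove it.

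**Conclusion.** The point holds as a gap in the design of Study three. As written, the protocol does not ensure that the eight cancer patients are stable between the forms, and treatment in the interval would enter both coefficients as disagreement. That it does fall there is likely, given the order of care the protocol describes, but it is an inference.

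The size depends wholly on assumed change. From a true ICC of 0.85, the patients' ICC would be about 0.66 with mean and spread of 0.5 SD, and about 0.47 with 0.8 SD. In a pooled analysis the fall may be hidden, or the pooled value may exceed the true within-group reliability. The consequence is confined to what the reliability study can conclude about patients. It does not by itself invalidate the Study one comparison. The change is worth making because it costs little and the information may not be recoverable afterwards.

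**What to change.** 1. Add to the retest form one question on any dental or oncological treatment since the first form, with its date.
2. Report ICC and CCC separately for patients and healthy controls, not only pooled over the 16.
3. Base the patients' stability estimate on pairs with no treatment in between. Show treated pairs separately, as change rather than unreliability.
4. If too few untreated patient pairs remain, state that patient test-retest reliability was not established.
5. Do not alter the timing of care to suit the retest.

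Moving the patients' retest to follow the 12-month form is not a clear improvement. The protocol allows fixed dentures to start at six months or later, and in severe cases measurement after one month of use, so a prosthesis may still be recent then.

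The cost is one question. The downside is fewer usable patient pairs, possibly very few of eight, and wide intervals: even all eight give 0.33 to 0.96 at an ICC of 0.80.

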Convergent validity: Spearman rank order correlations (ρ), assess convergent validity between (i) OHIP summary scores and self-reported health and (ii) OHIP subscale scores and subscale scores of the SF-36 and EQ-5D.

Study four – Cost-effectiveness analysis

Background

In order for a method in health- and dental care to be considered cost-effective, it has to be a decent relation between its extra costs and effects (no exact threshold value exist in Sweden). A cost-effectiveness analysis estimates the incremental cost-effectiveness ratio (ICER) of a method in comparison with the best option (33). The outcome measure can be of any (relevant) kind, but usually it is recommended to use quality-adjusted life-years (QALYs) which also is preferred by the Swedish Dental and Pharmaceutical Benefits Agency (34). QALY combines preferences for health states (QALY-weight) with the number of years of that health state.

In order to capture the full consequences of a treatment, it is often necessary to model future costs and effects into a longer time horizon. Even though these models cannot be seen as evidence, they can provide the most accurate estimate on the long-term cost-

effectiveness and they can furthermore handle uncertainty in order to provide a decision-maker with relevant information (35).

Data collection

Costs and effects of different prosthodontic rehabilitations, fixed and removable dentures, will be compared with costs and effects of radiotherapy of patients with head and neck cancer. Data on resource use will be gathered in the intervention and translated into costs, representing their best alternative use. Productivity loss of patients unable to work will be estimated using the human capital approach. The main outcome measure in the analysis will be QALY. QALY-weights are derived indirectly from the instruments EQ-5D and SF-6D, and directly from the EQ-VAS, all of which are analysed in Study one in this project. Other outcome measures that are more directly derived from oral health related quality of life will be used too in order to examine their relevance.

Data analysis

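### The retest sample is stated in two ways, and pooling the n=16 version would probably overstate reliability among cancer patients on OHIP-14 and GOHAI

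*Protocol*

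**What the plan says.** The Protocol describes the retest in two places.

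- **Participants:** "The retest described in data collection study one will include ten patients diagnosed with head and neck tumor", all of them resident in one county. No healthy people are mentioned. The sentence points to the data collection of Study one, but that section describes no retest.
- **Study three, Data collection:** "Eight patients with head and neck cancer from the Department of Maxillofacial and Oral Surgery (City of Jönköping), and eight healthy controls" are recruited, and after one to two weeks "those patients (n=16) will complete the same instruments to evaluate test-retest reliability and validity".

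Under Study three, Data analysis, the reliability measures are Cronbach's alpha ("Homogeneity: Cronbach's alpha assesses internal consistency"), an "ICC method based on a one-way analysis of variance (ANOVA"), and the CCC for stability over time. None of the three is given its own sample, a group term or a restriction to patients. Discriminative validity compares patients with controls on OHIP-14 and GOHAI: "Relevant and statistically significant differences using t-tests and ANOVA are expected". For convergent validity, "Spearman rank order correlations (ρ), assess convergent validity" between OHIP and other health measures, again with no sample named.

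In Study one both groups are cancer patients. The 30 matched controls have the same disease as the 30 intervention patients.

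**The concern.** ICC and CCC compare the variation between subjects with the variation within them. If two groups with different means are put into one calculation without a group term, the gap between the groups enters as variation between subjects. The coefficient can then look good because the instrument separates ill from healthy people, even if it separates one cancer patient from another poorly. Study one needs the second ability, since it has no healthy arm. Study three itself predicts a gap on two of the scales.

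Design and setting counts the methodological study among the elements meant to strengthen the case-control study in place of a power calculation. A reliability figure that describes a different population gives weaker support than it appears to.

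**Working it through.** **Head count.** 8 + 8 = 16, which agrees with the n in Study three. It does not agree with the ten tumour patients under Participants, either in number or in kind. The Protocol gives no ICC, SD or group difference, so every value of ρ, d and SD ratio below is an assumption.

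**Size of the gap.** The Protocol expects a significant difference but gives no size. With 8 v 8 and two-sided 0.05 (sidedness is assumed), the smallest observed standardised difference that is significant is t(0.975; 14 df) × √(2/8) = 2.145 × 0.5 = 1.07. This serves as a reference value for d, within a range.

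**Pooled ICC, equal variances.** Let ρ be the ICC among patients and d the gap in within-group SDs. Two equal groups add d²/4 to the between-subject variance:

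pooled ICC = (ρ + d²/4) / (1 + d²/4)

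At d = 1.07, d²/4 = 0.286. For ρ = 0.60: 0.886 / 1.286 = 0.689. For ρ = 0.70: 0.986 / 1.286 = 0.767.

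| ρ in patients | d = 0 | d = 0.5 | d = 0.8 | d = 1.07 | d = 1.5 |
|---|---|---|---|---|---|
| 0.60 | 0.600 | 0.624 | 0.655 | 0.689 | 0.744 |
| 0.70 | 0.700 | 0.718 | 0.741 | 0.767 | 0.808 |
| 0.80 | 0.800 | 0.812 | 0.828 | 0.845 | 0.872 |

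The same form holds for the CCC if there is no systematic shift at retest. In 4,000 simulated samples of 8 + 8 at d = 1.07, the median ICC and CCC were 0.695 and 0.681 for ρ = 0.60, and 0.770 and 0.759 for ρ = 0.70.

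**Unequal variances.** Suppose healthy scores have 0.65 times the patients' SD and the same error variance, with ρ = 0.60 and d in patient SDs. The error variance is 0.40, and the healthy true variance is 0.65² − 0.40 = 0.0225. The between-subject variance is (0.60 + 0.0225)/2 + d²/4 = 0.311 + d²/4.

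- d = 0.8: 0.471 / 0.871 = 0.54
- d = 1.07: 0.597 / 0.997 = 0.60
- d = 1.5: 0.874 / 1.274 = 0.69

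The pooled value is thus below, equal to or above the patient value, depending on d. If the healthy error variance shrinks in proportion instead, so that both groups have ICC 0.60, the pooled values are 0.67, 0.72 and 0.78.

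**Precision.** The exact F interval for a one-way ICC with two measurements starts from F = (1 + ICC)/(1 − ICC). For an observed 0.70, F = 1.70/0.30 = 5.67. The limits are (F_L − 1)/(F_L + 1) and (F_U − 1)/(F_U + 1), where F_L = F / F(0.975; n−1, n) and F_U = F × F(0.975; n, n−1).

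| n | 95% CI for observed ICC 0.70 |
|---|---|
| 8 | 0.11 to 0.93 |
| 10 | 0.20 to 0.91 |
| 16 | 0.34 to 0.88 |

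**The case against.** The strongest reply is that pooling is never stated. The figure 16 counts the people who complete the forms twice, the reliability paragraph names no sample, and where Study three does address groups it keeps them apart. Under the Participants version there are no healthy controls and the problem disappears. Whether coefficients are reported overall or by group could also be left to a statistical analysis plan. This stands to the extent that pooling must be called the natural reading and not a fact. It does not remove the point: the Protocol itself fixes the retest sample in two incompatible ways, and it fixes an ICC model with no group term. One could suppose two separate retests, but only one is described.

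Three stronger readings are tempting, and the documents do not support them.

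- **Every coefficient on every scale is inflated.** An expected gap is stated only for OHIP-14 and GOHAI. Baseline precedes any treatment, so very large gaps have no basis in the text. If healthy scores vary much less, pooling can leave the ICC unchanged or lower it.
- **Alpha and the convergent correlations are also computed on the mixture.** Their sample is not given. This is an ambiguity to close, not a demonstrated error.
- **Unreliable scales would be passed and Study one would suffer.** The Protocol sets no ICC or CCC threshold and no rule to keep or drop an instrument. Its only benchmark concerns alpha. It describes the instruments as already validated or tested, and no Study one comparison changes.

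It is also fair to object that a patient-only ICC from eight people says little. That is true, but a narrower interval around a quantity that does not describe the patients is no remedy.

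**Conclusion.** The point holds in a limited form. The contradiction between ten tumour patients and eight patients plus eight healthy controls is on the page and needs no assumption. If the 16 are pooled, as Study three most naturally reads, the ICC and CCC for OHIP-14 and GOHAI are likely to overstate reliability among cancer patients. The rise is about 0.09 from a patient ICC of 0.60 and about 0.07 from 0.70, assuming equal variances and d = 1.07. It is about 0.02 at d = 0.5, and 0.14 and 0.11 respectively at d = 1.5. The direction is likely but not guaranteed. In either direction, the pooled figure is not in general the reliability among patients. The matter concerns what Study three can claim about the instruments, and it does not invalidate Study one's comparison of treatments.

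**What to change.** - Reconcile Participants and Study three so that one retest sample is stated, with its number and composition.
- Report ICC and CCC for cancer patients separately from healthy controls, and do not use a pooled n=16 coefficient as the reliability estimate.
- Keep healthy controls for discriminative validity.
- Compute Cronbach's alpha and the convergent correlations in cancer patients, from the Study one baseline forms (up to 30 + 30 = 60 patients). Neither needs a retest.

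This changes wording only and needs no new data. The cost is precision: the patient-only retest interval is much wider than the pooled one, as shown above, and the coefficients may look less favourable. The interval should be reported openly, with a statement that the retest is too small to settle reliability among patients. Optionally, add the standard error of measurement.

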In this project, an interventional case-control study will be undertaken in four middle sized counties in the south of Sweden. Based on the case control sample also a methodological study will be realized in order to test the measurements' validity and reliability, but also a descriptive qualitative content analysis study will be accomplished. All these measurements – called triangulation – are done in order to strengthen the case-control study as a power calculation is not relevant to do due to the restricted eligible/consecutive sample as well as the restricted time schedule. Finally, based on all available data, a cost-effectiveness analysis will be undertaken with the use of a decision analytic model.

Intervention

Standard treatment

In order to replace extracted teeth after radiotherapy, the standard treatment is temporary removable dental prostheses/dentures (partial or complete). Depending on the teeth remaining, those may be completely tooth or tissue supported, or tissue and tooth supported. Temporary partial dentures are completely out of acrylic. Efforts are made to design a self-cleansing partial denture that preserves the remaining teeth and oral structures. The chewing forces are distributed evenly over the entire remaining teeth and soft tissues. Oral health related quality of life in healthy patients wearing removable dentures has previously been shown (12).

Fixed dentures

The special treatment is to within a year after completed radiotherapy replace removable dentures with tooth- or implant-supported dentures. The special treatment will begin six months after completed radiotherapy, or later depending on the severity of the side effects. Tooth- and implant-supported dentures are accepted modalities in patients with total or partial edentulous (13, 14). Patients with head and neck cancers usually follow the dental implant protocol valid for healthy individuals (15, 16). However, the fixture installation will be within a year after finished radiotherapy, when the jaws are still well supplied.

Participants

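### The Study three content-validity item asks whether the aesthetics questions match the patient's concerns but records the answer on a satisfaction scale, so the rating is ambiguous

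*Protocol*

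**What the plan says.** The Protocol's Design and setting section announces that "a methodological study will be realized in order to test the measurements' validity and reliability". This is Study three. Its Data collection section recruits eight patients with head and neck cancer and eight healthy controls, and says that "The instruments described in study one will be completed at baseline". By the Study one list, these are SF-36v2, EQ-5D, OHIP-14, GOHAI, JFLS-8 and OAS.

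Under Validity, the content-validity check is a single question: "Do you think the questions on aesthetics reflect the concerns you have with your mouth, your teeth and your tooth replacements". The answer format follows directly: "They respond on a 0–10 VAS-scale with the anchors “very dissatisfied” and “very satisfied".

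Two other validity checks are named. Discriminative validity uses OHIP-14 and GOHAI: "Comparisons are made of OHIP-14 and GOHAI summary scores of each patient group with control groups and between patient groups". Convergent validity correlates OHIP scores with self-reported health, SF-36 and EQ-5D.

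**The concern.** A content-validity rating should say how well a set of items covers what matters to the respondent. Here the stem asks that, but the two ends of the scale express satisfaction, and neither end is an answer to the question. The stem also names the mouth, the teeth and tooth replacements immediately before the respondent marks the line, which invites a rating of those instead of a rating of the questionnaire.

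The respondents make this a practical matter. Under Participants, the included patients have dental infections and planned extractions, and Study three takes its first measurement at baseline. Such a patient may find the aesthetics items entirely relevant and still mark the dissatisfied end.

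What is at stake is whether the content-validity result can be read at all clearly. It is also the only validity check that Study three names for the OAS. Because the Protocol itself fixes the wording and the anchors, an analysis plan cannot repair the answers once they are collected.

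**Working it through.** No arithmetic applies and the Protocol states no figure to reproduce. The check sets the relevant parts of the text side by side.

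**1. Question against anchors (Study three, Validity).**

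| Element | What it measures |
|---|---|
| Stem: "Do you think the questions on aesthetics reflect the concerns you have with your mouth" | Relevance of the items |
| Anchors of the 0–10 scale | Degree of satisfaction, object not stated |

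**2. What a mark can mean.**

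| Mark | If the respondent rates the questionnaire | If the respondent rates the mouth or teeth |
|---|---|---|
| Low | The items miss the concerns | The patient is unhappy with mouth or teeth; nothing follows about the items |
| High | The items cover the concerns | The patient is content with mouth or teeth; nothing follows about the items |

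Nothing else recorded with the mark shows which column applies. No other part of the Protocol corrects the anchors or adds a second item that would separate the two readings.

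**3. Which instrument is rated.** The stem refers to aesthetics. Of the six Study one instruments, only one is described as an aesthetics scale: "The OAS consists of seven separate aesthetic aspects of the face, teeth, lips, and mouth". The item therefore concerns 1 of 6 instruments.

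**4. How many respondents.** The text says that patients are asked. Read strictly, that is the 8 cancer patients. The same section also uses the word patients for all participants, 8 + 8 = 16. The number of affected ratings is thus 8 or 16. (The Participants section separately mentions a retest in ten patients, which it attaches to Study one. The present point does not depend on how the two are reconciled.)

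**5. Where the rating is used.** It does not appear in the Study one data analysis, the Study two content analysis or the Study four cost-effectiveness model. No acceptance threshold is attached to it.

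**The case against.** The strongest reply is that the scale follows directly on a question about the questionnaire, so a respondent may well take it as satisfaction with how well the questions capture the concerns. On that reading the item works, if clumsily. This stands to the extent that the rating is ambiguous and not empty; a reader might infer that it is uninterpretable, and the text does not support going so far. The patient form is not shown and the English wording may be a paraphrase of a Swedish original, but this cannot be verified from the Protocol.

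A reader might also infer a second defect: that OHIP-14, GOHAI and JFLS-8 wrongly lack a content-validity rating, although the project aim concerns "prosthodontic rehabilitation on oral health related quality of life, general wellbeing, and nutrition in patients treated by radiotherapy" and does not name aesthetics. The Protocol does not support this as an error. It assigns different checks to different scales, never promises content validity for each one, and cites earlier Swedish validation for five instruments and reliability and validity testing for JFLS-8. Restricting the item to aesthetics is a choice of scope. What remains is that the result should be labelled accordingly.

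A third tempting inference is that patients will score low and healthy controls high. This is conjecture. It assumes that respondents ignore the stem, and the Protocol plans no comparison of this rating between groups; the only group comparisons in Study three concern OHIP-14 and GOHAI.

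Finally, the result is secondary and descriptive. That is correct and limits the weight of the point, but the correction costs almost nothing.

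**Conclusion.** The mismatch between question and anchors is real and can be read directly from the text. As written, the content-validity rating cannot distinguish items that miss the patient's concerns from a patient's unhappiness with mouth or teeth. The size is one descriptive result in Study three, from 8 or 16 respondents, about one instrument.

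The conclusion assumes that the form given to respondents carries the anchors as the Protocol words them. It does not depend on how many respondents would misread the scale, since the ambiguity arises whenever some might.

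The documents do not support reading this as a flaw in the outcome scales, in the Study one comparison or in the Study four model. Nor do they establish that all 16 ratings are affected.

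**What to change.** - Replace the anchors with ones that answer the question, such as *not at all* (0) and *completely* (10).
- State that the content-validity result applies to the OAS only, and say whether the healthy controls answer the item.
- Optionally, if content validity is to be claimed for OHIP-14, GOHAI and JFLS-8, repeat the item after each of them, with *these questions* in place of the reference to aesthetics, and report the ratings by instrument.

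Check the patient form first: if its anchors already answer the question, only the Protocol text needs correcting. If ratings have already been collected on the satisfaction anchors, report them with the anchors shown and the ambiguity stated.

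The cost is one form revision, plus up to three single-line items if the check is extended. No extra visits or patients are needed.
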